5.6.1.1.16 Hematologic Events

Subjects should be carefully monitored for signs and symptoms of hematologic events (such as autoimmune hemolytic anemia, aplastic anemia, disseminated intravascular coagulation (DIC), or neutropenia). All attempts should be made to rule out other causes such as metastases, sepsis and/or infection. Relevant diagnostic studies such as peripheral blood smear, reticulocyte count, LDH, haptoglobin, bone marrow biopsy or Coomb’s test, etc., should be considered to confirm the diagnosis. However the AE should be reported regardless of etiology.

Dose modification and supportive care guidelines for hematologic adverse events are described in [Table 31](#). Guidelines for dose modification for neutropenia are provided in [Table 32](#).

Table 31 Management and Dose Modification Guidelines for Hematologic Adverse Events

CTCAE Grade	Adverse Event Management	Action and Dose Modification
Grade 2	
 Consider Hematology consultation Consider systemic corticosteroids at a dose of 1 to 2 mg/kg/day prednisone or equivalent. When symptoms improve to Grade 1 or less, steroid taper (if systemic corticosteroids initiated) should be started and continued over no less than 4 weeks. 	
 Interrupt pembrolizumab until improvement to \leqGrade 1 Consider interruption of dabrafenib and/or trametinib
Grade 3	
 Hematology consultation Treat with methylprednisolone 125mg IV or prednisone 1-2 mg/kg p.o. (or equivalent) as appropriate. When symptoms improve to Grade 1 or less, steroid taper (if systemic corticosteroids initiated) should be started and continued over no less than 4 weeks. 	
 Interrupt all study treatment until improvement to \leqGrade 1 Restart dabrafenib and/or trametinib at reduced dose
Grade 4	
 Same as grade 3 	
 Permanently discontinue all study treatment

Abbreviations: CTCAE = Common Terminology Criteria for Adverse Events

Table 32 Management and Dose Modification Guidelines for Neutropenia

CTCAE Grade	Action and Dose Modification
Grade 2	
 Consider interrupting dabrafenib and/or trametinib if clinically indicated Monitor closely Provide supportive care according to institutional standards When toxicity resolves to \leqGrade 1, restart study treatment at current dose level
Grade 3	
 Interrupt dabrafenib and/or trametinib Monitor closely Provide supportive care according to institutional standards When toxicity resolves to \leqGrade 1, restart dabrafenib and/or trametinib at reduced dose. May titrate dose up to previous level if tolerated
Grade 4	
 Interrupt all study treatment Monitor closely Provide supportive care according to institutional standards When toxicity resolves to \leqGrade 1, restart pembrolizumab at current dose. Restart dabrafenib and/or trametinib at reduced dose. May titrate dose up to previous level if tolerated If the Grade 4 toxicity recurs, either permanently discontinue all study treatment or, if the subject is clinically benefitting, discuss continuation of treatment with the Sponsor
Abbreviations: CTCAE = Common Terminology Criteria for Adverse Events	

5.6.1.1.17 Neurologic Events

Subjects should be carefully monitored for signs and symptoms of neurologic events. All attempts should be made to rule out other causes such as metastatic disease, other medications or infectious causes. However the AE should be reported regardless of etiology.

Dose modification and supportive care guidelines for neurologic adverse events are described in [Table 33](#).

Table 33 Management and Dose Modification Guidelines for Neurologic Adverse Events

CTCAE Grade	Adverse Event Management	Action and Dose Modification
Grade 2	
 Consider Neurology consultation and possible biopsy for diagnosis Consider systemic corticosteroids at a dose of 1 to 2 mg/kg/day prednisone or equivalent. When symptoms improve to Grade 1 or less, steroid taper (if systemic corticosteroids initiated) should be started and continued over no less than 4 weeks. 	
 Consider interrupting pembrolizumab
Grade 3	
 Neurology consultation and consider biopsy for diagnosis Treat with systemic corticosteroids prednisone 1-2 mg/kg p.o. (or equivalent). If condition worsens consider IVIG or other immunosuppressive therapies as per local guidelines. When symptoms improve to Grade 1 or less, steroid taper (if systemic corticosteroids initiated) should be started and continued over no less than 4 weeks. 	
 Permanently discontinue pembrolizumab Consider interrupting dabrafenib and/or trametinib
Grade 4	
 Same as grade 3 	
 Permanently discontinue pembrolizumab Consider interrupting dabrafenib and/or trametinib
Abbreviations: CTCAE = Common Terminology Criteria for Adverse Events		

5.6.1.1.18 Infusion Reactions

Subjects should be carefully monitored for signs and symptoms of infusion reaction (such as allergic reaction, anaphylaxis, cytokine release syndrome, or serum sickness). The AE should be reported regardless of etiology.

Signs and symptoms usually develop during or shortly after drug infusion and generally resolve completely within 24 hours of completion of infusion.

5.6.1.2 Pembrolizumab Infusion Reaction Treatment Guidelines

Pembrolizumab may cause severe or life-threatening infusion-reactions including severe hypersensitivity or anaphylaxis. Signs and symptoms usually develop during or shortly after drug infusion and generally resolve completely within 24 hours of completion of infusion. Dose modification and toxicity management guidelines on pembrolizumab associated infusion reaction are provided in [Table 34](#).

Pembrolizumab subjects should receive appropriate supportive care measures as deemed necessary by the treating investigator including but not limited to the items outlined below:

- **Management of Infusion Reactions:** acute infusion reactions (which can include cytokine release syndrome, angioedema, or anaphylaxis) are different from allergic/hypersensitive reactions, although some of the manifestations are common to both AEs. Signs and symptoms usually develop during or shortly after drug infusion and generally resolve completely within 24 hours of completion of infusion. Signs/symptoms may include: allergic reaction/hypersensitivity (including drug fever); arthralgia (joint pain); bronchospasm; cough; dizziness; dyspnea (shortness of breath); Fatigue (asthenia, lethargy, malaise); Headache; Hypertension; hypotension; myalgia (muscle pain); nausea; pruritis/itching; rash/desquamation; rigors/chills; sweating (diaphoresis); tachycardia; tumor pain (onset or exacerbation of tumor pain due to treatment); urticaria (hives, welts, wheals); vomiting.

Table 34 Pembrolizumab Infusion Reaction Dose Modification and Treatment Guidelines

NCI CTCAE Grade	Treatment	Premedication at Subsequent Dosing

Grade 1 Mild reaction; infusion interruption not indicated; intervention not indicated
	
Increase monitoring of vital signs as medically indicated until the subject is deemed medically stable in the opinion of the investigator.
	
None


Grade 2 Requires infusion interruption but responds promptly to symptomatic treatment (e.g., antihistamines, NSAIDS, narcotics, IV fluids); prophylactic medications indicated for ≤24 hrs
	
Stop Infusion. Additional appropriate medical therapy may include but is not limited to: IV fluids Antihistamines NSAIDS Acetaminophen Narcotics
 
Increase monitoring of vital signs as medically indicated until the subject is deemed medically stable in the opinion of the investigator.
 
If symptoms resolve within 1 hour of stopping drug infusion, the infusion may be restarted at 50% of the original infusion rate (e.g. from 100 mL/hr to 50 mL/hr). Otherwise dosing will be held until symptoms resolve and the subject should be premedicated for the next scheduled dose.
 
Subjects who develop Grade 2 toxicity despite adequate premedication should be permanently discontinued from further trial treatment administration.
	
Subject may be premedicated 1.5h (± 30 minutes) prior to infusion of pembrolizumab with: Diphenhydramine 50 mg po (or equivalent dose of antihistamine). Acetaminophen 500-1000 mg po (or equivalent dose of analgesic).

NCI CTCAE Grade	Treatment	Premedication at Subsequent Dosing

Grades 3 or 4
 
Grade 3: Prolonged (i.e., not rapidly responsive to symptomatic medication and/or brief interruption of infusion); recurrence of symptoms following initial improvement; hospitalization indicated for other clinical sequelae (e.g., renal impairment, pulmonary infiltrates)
 
Grade 4: Life-threatening; pressor or ventilatory support indicated
	
Stop Infusion.
 
Additional appropriate medical therapy may include but is not limited to:
 
 IV fluids Antihistamines NSAIDS Acetaminophen Narcotics Oxygen Pressors Corticosteroids Epinephrine** 
Increase monitoring of vital signs as medically indicated until the subject is deemed medically stable in the opinion of the investigator.
 
Hospitalization may be indicated.
 
**In cases of anaphylaxis, epinephrine should be used immediately.
 
Subject is permanently discontinued from further trial treatment administration.
	
No subsequent dosing


Appropriate resuscitation equipment should be available at the bedside and a physician readily available during the period of drug administration.
 
For Further information, please refer to the Common Terminology Criteria for Adverse Events v4.0 (CTCAE) at http://ctep.cancer.gov
 
IV=intravenous; NSAIDs= non-steroidal anti-inflammatory drugs; PO=oral administration.
		

5.6.1.3 Supportive Care Guidelines for Adverse Events with an Immune-Etiology (irAEs)

Adverse events of a potential immunologic etiology (irAEs) may be defined as an adverse event of unknown etiology, associated with drug exposure and is consistent with an immune phenomenon. irAEs may be predicted based on the nature of the pembrolizumab compound, its mechanism of action, and reported experience with immunotherapies that have a similar mechanism of action. Special attention should be paid to AEs that may be suggestive of potential irAEs. An irAE can occur shortly after the first dose or several months after the last dose of treatment.

If an irAE is suspected, efforts should be made to rule out neoplastic, infectious, metabolic, toxin or other etiologic causes prior to labeling an adverse event as an irAE. Subjects who develop a Grade 2 or higher irAE should be discussed immediately with the Sponsor.

Recommendation to evaluate and manage irAEs are provided in Section 5.6.1.1.3 and Section 5.2.1.2.1, [Table 10](#). Recommendations to managing irAEs that are not detailed elsewhere in the protocol are detailed in [Table 35](#).

Table 35 General Approach to Handling irAEs

irAE	Withhold/Discontinue Pembrolizumab?	Supportive Care
Grade 1	No action	Provide symptomatic treatment
Grade 2	May withhold pembrolizumab	Consider systemic corticosteroids in addition to appropriate symptomatic treatment
Grade 3 and Grade 4	Withhold pembrolizumab Discontinue if grade 4 or grade 3 and unable to reduce corticosteroid dose to < 10 mg per day prednisone equivalent within 12 weeks of toxicity	Systemic corticosteroids are indicated in addition to appropriate symptomatic treatment. May utilize 1 to 2 mg/kg prednisone or equivalent per day. Steroid taper should be considered once symptoms improve to Grade 1 or less and tapered over at least 4 weeks.

5.7 Diet/Activity/Other Considerations

5.7.1 Diet

Subjects should maintain a normal diet unless modifications are required to manage an AE such as diarrhea, nausea or vomiting.

5.7.2 Contraception

Pembrolizumab and other study medications may have adverse effects on a fetus in utero. Refer to Appendix 12.14 for approved methods of contraception.

Participants should be informed that taking the study medication may involve unknown risks to the fetus (unborn baby) if pregnancy were to occur during the study. In order to participate in the study, participants of childbearing potential must adhere to the contraception requirement (Appendix 12.14) from the day of study medication initiation throughout the study period up to 120 days after the last dose of study medication. If there is any question that a participant of childbearing potential will not reliably comply with the requirements for contraception, that participant should not be entered into the study.

5.7.3 Use in Pregnancy

If a female subject inadvertently becomes pregnant while on treatment with pembrolizumab or trametinib or dabrafenib, the subject will immediately be removed from the study. The site will contact the subject at least monthly and document the subject's status until the pregnancy has been completed or terminated. The outcome of the pregnancy will be reported to the Sponsor without delay and within 24 hours if the outcome is a serious adverse

experience (e.g., death, abortion, congenital anomaly, or other disabling or life-threatening complication to the mother or newborn). The study investigator will make every effort to obtain permission to follow the outcome of the pregnancy and report the condition of the fetus or newborn to the Sponsor. If a male subject impregnates his female partner the study personnel at the site must be informed immediately and the pregnancy reported to the Sponsor and followed as described above and in Section 7.2.2.

5.7.4 Use in Nursing Women

It is unknown whether pembrolizumab or trametinib or dabrafenib is excreted in human milk. Since many drugs are excreted in human milk, and because of the potential for serious adverse reactions in the nursing infant, subjects who are breast-feeding are not eligible for enrollment.

5.8 Subject Withdrawal/Discontinuation Criteria

5.8.1 Discontinuation of Treatment

Discontinuation of treatment does not represent withdrawal from the trial.

As certain data on clinical events beyond treatment discontinuation may be important to the study, they must be collected through the subject's last scheduled follow-up, even if the subject has discontinued treatment. Therefore, all subjects who discontinue trial treatment prior to completion of the treatment will still continue to participate in the trial as specified in Section 6.0 - Trial Flow Chart and Section 7.1.5.3 – Post-Treatment Follow-Up Phase.

Subjects may discontinue treatment at any time for any reason or be dropped from treatment at the discretion of the investigator should any untoward effect occur. In addition, a subject may be discontinued from treatment by the investigator or the Sponsor if treatment is inappropriate, the trial plan is violated, or for administrative and/or other safety reasons. Specific details regarding procedures to be performed at treatment discontinuation are provided in Section 7.1.4 – Other Procedures.

A subject must be discontinued from treatment but continue to be monitored in the trial for any of the following reasons:

- The subject or legal representative (such as parent or legal representative) withdraws consent.
- The subject's treatment assignment has been unblinded by the investigator, Merck subsidiary or through the emergency unblinding call center.
- The subject has a medical condition or personal circumstance which, in the opinion of the investigator and/or sponsor, placed the subject at unnecessary risk from continued administration of study drug/vaccine

- The subject has a confirmed positive serum pregnancy test.
- Documented disease progression

Note: If a subject has confirmed progression of disease, i.e., persistent tumor increase of 20% or greater compared to nadir and/or worsening or increased number of new lesions, (via a second scan at least 28 days from the date of the scan showing initial radiological progression by RECIST 1.1), the subject should not receive further trial treatment on study. If a subject has unconfirmed progression of disease and is clinically stable, it is at the discretion of the investigator to continue treating the subject with the assigned treatment per protocol until progression of disease is confirmed at least 28 days from the date of the scan suggesting progression of disease. Clinical Stability is defined as:

- 1) Absence of symptoms and signs indicating clinically significant progression of disease (including worsening of laboratory values) indicating disease progression.
 - 2) No decline in ECOG performance status.
 - 3) Absence of rapid progression of disease or progressive tumor at critical anatomical sites (e.g., cord compression) requiring urgent alternative medical intervention.
- Unacceptable adverse experiences as described in Section 5.2.1.2 and Section 5.6
 - Intercurrent illness that prevents further administration of treatment
 - Investigator's decision to withdraw the subject
 - Noncompliance with trial treatment or procedure requirements
 - The subject is lost to follow-up
 - Administrative reasons

The End of Treatment and Follow-up visit procedures are listed in Section 6 - Trial Flow Chart and Section 7.1.5 - Visit Requirements. After the end of treatment, each subject will be followed for a minimum of 30 days for adverse event monitoring (serious adverse events will be collected for up to 90 days after the end of treatment as described in Section 7.2.3.1). Subjects will have post-treatment follow-up for disease status until disease progression, initiating a non-study cancer treatment, withdrawing consent, or becoming lost to follow-up. After documented disease progression each subject will be followed for overall survival until death or withdrawal of consent, or the end of the study, whichever occurs first.

Discontinuation of pembrolizumab after CR

Discontinuation of pembrolizumab may be considered for subjects who have attained a confirmed response per RECIST 1.1 that have been treated for at least 6 months and had at least two doses of pembrolizumab treatment beyond the date when the initial CR was declared. See Section 5.2.5 for more information.

For subjects who are discontinued from treatment but continue to be monitored in the trial, all visits and procedures, as outlined in the trial flowchart, should be completed.

Subjects may be allowed to begin treatment again if deemed medically appropriate..

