After radiological assessment at screening, the first radiological assessment will be performed following 2 cycles of study treatment (± 7 days), unless there is clinical indication (based on Investigator's assessment) warranting earlier radiologic imaging. The same imaging technique as used at screening should be used throughout the study. After the first on-treatment imaging assessment, subjects will be evaluated every six (6) weeks up to Month 18 with radiographic imaging to assess response to treatment. Following Month 18, imaging assessment will occur every twelve (12) weeks. Investigators will make all treatment-based decisions using modified Response Evaluation Criteria in Solid Tumors (RECIST) 1.1 criteria. Imaging from Parts 1, 2, 4, and 5 for (MK+D+T) and (MK+T) and Part 3 (non-inclusive of IA) will be investigator-assessed using RECIST 1.1 for determination of endpoints (including ordinal response), but also collected and held, and may be centrally-read later by independent radiologists, retrospectively. Imaging for the first 80 patients up to Week 36 in Part 3 (subjects included in the interim analysis) will be centrally-read using RECIST 1.1 for determination of efficacy endpoints. Refer to Section 8.2.3 for additional information on endpoints. RECIST 1.1 will be adapted as described in Section 4.2.3.1 due to the tumor response patterns seen with pembrolizumab treatment (e.g., tumor flare), and this

adapted RECIST will be used by the sites for treatment decisions. Adverse events will be monitored throughout the trial and graded in severity according to the guidelines outlined in the NCI Common Terminology Criteria for Adverse Events (CTCAE) Version 4.0. In general, study treatment will continue until documented disease progression, unacceptable adverse event(s), intercurrent illness that prevents further administration of treatment, investigator's decision to withdraw the subject, subject withdraws consent, pregnancy of the subject, noncompliance with trial treatment or procedure requirements, or administrative reasons. Subjects who attain an investigator-determined confirmed complete response (CR) per RECIST after at least 6 months of pembrolizumab treatment could potentially stop trial treatment of pembrolizumab and continue treatment with trametinib and/or dabrafenib, in accordance with standard care, until disease progression or the end of study, whichever comes first.

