4.2.3 Rationale for Endpoints

4.2.3.1 Efficacy Endpoints

4.2.3.1.1 Primary

The primary efficacy endpoint of the trial is Progression Free Survival (PFS) in Part 3. PFS is an acceptable scientific endpoint to demonstrate superiority of a new antineoplastic therapy, especially if it is believed that the median time to Overall Survival (OS) with the new therapy may be significantly longer than that seen with standard of care. RECIST 1.1 will be used to determine the dates of progression as this methodology is accepted by regulatory authorities. Images will be read by investigators and collected and held for potential central-read by independent radiologists later, as determined by the Sponsor.

For the (MK+T) cohort, the primary efficacy endpoint of the study is objective response rate (ORR) based on a best overall response (BOR) analysis in subjects with advanced or metastatic melanoma without BRAF mutation. Modified RECIST 1.1 (see discussion below) will be used to assess response rate by investigators/sites and collected and held for potential central-read by independent radiologists later, as determined by the Sponsor.

RECIST 1.1 will be adapted to account for the unique tumor response characteristics seen with treatment of pembrolizumab. Immunotherapeutic agents such as pembrolizumab may produce antitumor effects by potentiating endogenous cancer-specific immune responses. The response patterns seen with such an approach may extend beyond the typical time course of responses seen with cytotoxic agents and can manifest a clinical response after an initial increase in tumor burden or even the appearance of new lesions. Standard RECIST may not provide an accurate response assessment of immunotherapeutic agents such as pembrolizumab. Therefore, RECIST 1.1 will be used with the following adaptations:

If radiologic imaging shows initial PD, tumor assessment should be repeated ≥ 4 weeks later in order to confirm PD with the option of continuing treatment per below while awaiting radiologic confirmation of progression. If repeat imaging shows a reduction in the tumor burden compared to the initial scan demonstrating PD, treatment may be continued / resumed. If repeat imaging confirms progressive disease, subjects will be discontinued from study therapy. In determining whether or not the tumor burden has increased or decreased, investigators should consider all target lesions as well as non-target lesions (please refer to the Site Imaging Manual).

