18 On C1D22, both pre-dose and post-dose plasma samples for PK of trametinib and dabrafenib will be collected. On C1D22, morning dose(s) should be withheld until after PK (pre-dose) sample has been drawn. On C1D22, post-dose PK samples for trametinib and/or dabrafenib should be drawn (1) at the same time as when the post-dose pembrolizumab PK sample is drawn (the end of infusion), and, (2) at approximately 4-6 hours post-dose. On C2D1, subjects should take their morning dose at home. A post-dose sample will be obtained during study visit. Thereafter, PK plasma samples will be collected at Day 1 of every alternate cycle (i.e., Day 1 of Cycle 3, Day 1 of Cycle 5, etc.) during study visit. If visit is in the morning, subjects will be asked to withhold their morning dose; if visit is in the afternoon, subjects will be asked to take their morning dose as usual. Procedures for collection of samples are described in the Procedures Manual.

19 The initial tumor imaging will be performed within 28 days prior to the date of allocation. Scans performed as part of routine clinical management are acceptable for use as the screening scan if they are of diagnostic quality and performed within 28 days prior to the first dose of trial treatment. CT scans are the required modality for measurable disease unless a subject has a clinical condition, e.g., severe contrast allergy. The same imaging technique has to be used for the subject throughout the study. The visit window for subsequent imaging is ± 7 days. If there is progressive disease, radiologic assessment/tumor imaging should be obtained at least four weeks from scan date for confirmation. CT timing should follow calendar days and should not be adjusted for delays in cycle starts. Response status will be assessed by the investigator. The process for collection of CT images is described in the Procedures Manual. Tumor imaging will be performed every 6 weeks (or whenever clinically indicated) starting at Week 13 while the subject remains on study therapy; after 18 months, tumor imaging will be performed every 12 weeks (or whenever clinically indicated) while the subject remains on study therapy. Per the modified RECIST 1.1 used in this protocol, if imaging shows progressive disease, the imaging assessment should be repeated at a minimum of 4 weeks later in order to confirm progressive disease as described in Section 4.2.3.1.

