Percentage of Subjects with PR based upon RECIST 1.1 by the investigator review

Percentage of Subjects with Deep Response (DR) where DR is a response that is either CR or VGPR by the investigator review.

Best Target Lesion Response - maximum percent reduction in tumor line length over target lesions by the investigator review.

Time to Confirmed Response – defined only for subjects with confirmed response by the investigator review. The time interval between the date of randomization and the date of the first confirmed response (CR/PR) (the response prior to confirmation).

Percentage of Subjects with Sustained Response at Week 36 (used in the interim analysis) - subjects who achieved response (confirmed CR or PR) prior to Week 36 but have not yet progressed at Week 36 by central review.

Tumor growth kinetics endpoints: growth rate constant (GST) and time-to-growth (TTG) and other as appropriate. These endpoints will be used in Modeling and Simulations analysis.

EuroQol (EQ-5D) and EORTC (QLQ-C30) endpoints

Additional supportive analyses of PFS, objective response rate, best overall response, and duration of response will be conducted using modified RECIST 1.1 criteria, in which a confirmation assessment of disease progression must be obtained at least 4 weeks after the initial disease assessment indicating progressive disease.

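### Section 4.2.3.1.1 permits treatment after some repeat scans that Section 5.8.1 counts as confirmed progression, and the modified-RECIST analyses do not say how such patients are classified or dated

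*Combined protocol and SAP*

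**What the plan says.** Section 5.8.1 lists documented progression among the reasons for stopping treatment. Its note spells out confirmed progression as "persistent tumor increase of 20% or greater compared to nadir and/or worsening or increased number of new lesions", seen on a second scan at least 28 days after the scan that first showed PD. For such a subject the consequence is that "the subject should not receive further trial treatment on study".

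Section 4.2.3.1.1 adapts RECIST 1.1 and asks for a repeat scan at least four weeks after initial PD. It gives two outcomes:

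- "If repeat imaging shows a reduction in the tumor burden compared to the initial scan demonstrating PD, treatment may be continued / resumed".
- Study therapy ends where the second scan confirms PD.

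It states no criterion for the second outcome. On tumor burden it adds "In determining whether or not the tumor burden has increased or decreased, investigators should consider all target lesions as well as non-target lesions", and refers to a Site Imaging Manual.

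Section 2.1 points to 4.2.3.1 for the adaptation and says this "adapted RECIST will be used by the sites for treatment decisions". In the Part 3 flow chart (Section 6.1.2, footnote 19), "the imaging assessment should be repeated at a minimum of 4 weeks later in order to confirm progressive disease as described in Section 4.2.3.1". The imaging footnotes in 6.1.1, 6.1.3, 6.1.4 and 6.2 give the same direction. Sections 4.2.3.1.1 and 5.8.1 do not cite each other.

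Section 8.2.3.1.3 plans supportive analyses of PFS, objective response rate, best overall response and duration of response by modified RECIST, in which "a confirmation assessment of disease progression must be obtained at least 4 weeks after the initial disease assessment indicating progressive disease". It names neither the reference scan nor the date at which a confirmed progression counts.

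**The concern.** The two sections judge the same repeat scan against different references: the nadir in 5.8.1 and the first PD scan in 4.2.3.1.1. A tumor can shrink from the first PD scan and still be at least 20% above nadir. For that patient, the section that sites are sent to permits treatment, while the section that lists the reasons for stopping says that treatment should end.

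The conflict carries into the supportive analyses. Depending on which section is read into Section 8.2.3.1.3, the patient has a confirmed progression or is still event-free. Later data may not settle it, because Section 6.3 moves a subject with progression to telephone survival follow-up, so the rule that a site applied can determine whether further scans exist.

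**Working it through.** There is no stated figure to reproduce. The check applies both rules to the same target-lesion sums.

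**Inputs.** Let N be the nadir sum, S1 the sum at the first PD scan (S1 at least 1.2N, PD called on target lesions) and S2 the sum at the repeat scan. The 20% threshold and the nadir reference come from 5.8.1; the comparison with the first PD scan comes from 4.2.3.1.1. All millimetre values and week numbers below are assumed for illustration.

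**Rules.**
- 5.8.1: PD is confirmed and treatment should stop if S2 ≥ 1.2N.
- 4.2.3.1.1: treatment may go on if S2 < S1.
- One permits what the other bars when 1.2N ≤ S2 < S1.

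**Example.** N = 50, S1 = 75, S2 = 65 mm.
- First PD: 75/50 = 1.50, a rise of 50%.
- Repeat against nadir: 65/50 = 1.30, so 5.8.1 is met.
- Repeat against first PD: 65 < 75, so 4.2.3.1.1 permits treatment.
- Conflict range: 1.2 × 50 = 60 mm up to just under 75 mm. Below 60 mm, 5.8.1 is not met on target sums and 4.2.3.1.1 permits treatment. At 75 mm or above, 5.8.1 is met and 4.2.3.1.1 gives no permission.

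**Width of the range.** If the first rise over nadir is x, the conflict covers shrinkage from the first PD scan of more than zero and up to 1 − 1.2/(1 + x):

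| Rise at first PD | Largest conflicting shrinkage |
|---|---|
| 20% | 0% (range empty) |
| 25% | 4.0% |
| 30% | 7.7% |
| 40% | 14.3% |
| 50% | 20.0% |
| 100% | 40.0% |

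**New lesions.** Suppose that PD was called on one new lesion, which is unchanged at the repeat scan with stable target lesions. The lesion has not worsened and the number has not risen, so the new-lesion wording of 5.8.1 is not clearly met. Section 4.2.3.1.1 sees no reduction, but does not say that no reduction means confirmed PD. Neither section clearly resolves this case.

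**Effect on modified-RECIST PFS.** Take first PD at Week 19, a conflicting repeat scan at Week 25 and later unequivocal PD at Week 37, with months = weeks × 7/30.4375.
- 5.8.1 reading: event at Week 19 (4.37 months), or at Week 25 (5.75 months) if dated at confirmation.
- 4.2.3.1.1 reading: event at Week 37 (8.51 months), or censoring if no later PD is seen.
- Difference when the later PD is seen: 37 − 19 = 18 weeks, or 37 − 25 = 12 weeks.

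The difference can also be small. With a repeat scan 4 weeks after first PD and death at 5 weeks, it is 5 weeks if dated at first PD and 5 − 4 = 1 week if dated at confirmation.

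**The case against.** The strongest reply is that 4.2.3.1.1 does not define confirmed progression at all. It gives a permission and leaves *confirms* open, so the only explicit definition is in 5.8.1, and an investigator who stops treatment complies with both. This is right as far as it goes: a reader might infer two competing definitions, and the text does not support that. But importing the 5.8.1 definition into 4.2.3.1.1 does not remove the conflict, because the permission covers any reduction, including one that stays above 1.2 times nadir. The closing sentence of 5.8.1, which allows treatment to begin again, stands under stopping after complete response and sets no benchmark for a repeat scan.

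Second, Section 2.1 and the flow charts tell sites to use 4.2.3.1, so sites are not choosing at random. That stands. It also means that the direction given to sites leads away from the discontinuation rule.

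Third, the range above uses target sums alone, while 4.2.3.1.1 also counts non-target lesions. That stands as a limit on the arithmetic.

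Fourth, the affected analyses are supportive, and Section 8.2 lets changes to exploratory analyses be explained in the study report. That limits the statistical weight, but does not settle who stays on treatment.

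The Site Imaging Manual may contain a rule, but it is not available here, and a contradiction between two protocol sections should be resolved in the protocol.

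**Conclusion.** The point holds as a contradiction between a permission and a bar. On target-lesion sums it arises whenever 1.2 × nadir ≤ repeat sum < first PD sum. It is absent when the first rise is exactly 20% and widens with the size of that rise. It rests on reading the two sections as written and on target sums standing for tumor burden.

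Four stronger readings are tempting and not supported:

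- **Primary PFS is compromised.** It is not. Section 8.2.3.1.1 uses RECIST 1.1 by investigator review, and Table 41 dates the event at documented PD or death without confirmation.
- **Each case shifts modified-RECIST PFS by at least six weeks.** A repeat scan may come at four weeks, death is an event, and no dating rule is given. Neither the size of the shift nor the number of patients can be derived from the documents.
- **The unchanged new lesion is a second contradiction.** It is a gap, since 4.2.3.1.1 is silent rather than opposed.
- **The inconsistency biased the Part 3 comparison.** Part 3 was double-blind and nothing in the documents shows imbalance from guessed assignment. Sections 5.2.5 and 7.1.5.3 already report its final analysis, so for that comparison the point bears only on interpreting the supportive results.

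What remains is worth correcting: treatment continuation for subjects still managed under this protocol, including Parts 4 and 5, and the meaning of the modified-RECIST results.

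**What to change.** Reconcile 4.2.3.1.1 and 5.8.1 into one definition of confirmed PD, with one named reference scan, one threshold and one rule for new lesions, including a new lesion that persists unchanged. The sponsor's clinical team must choose it; none is proposed here. Cite it in 4.2.3.1.1, 5.8.1 and the imaging footnotes of 6.1.1 to 6.1.4 and 6.2.

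In 8.2.3.1.3, cite the same definition and state the event date for the modified-RECIST analyses: the first PD scan or the confirming scan.

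The cost is protocol wording and a clarification to sites. No scans are added, because the repeat scan is already planned.
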